8.10 Response to the COVID19 global pandemic (Urgent Safety Measure)

During the COVID19 global pandemic, a thorough risk assessment was conducted, and as a result the following appropriate adaptations have been made to the delivery of the study:

- Face to face study visits may be replaced with virtual consultations via telephone call or video call via the MyClinic application. Verbal consent will be sought from participants in advance of the video consultation (via MyClinic) and will be documented in the medical records. Face to face visits may continue at sites if this is in accordance with the local trust policy and appropriate risk mitigations are implemented at site to reduce the risk to participants. Risk and mitigations will be detailed in the risk assessment. During this period both face to face visits and virtual ones may be conducted in line with the USM adaptations detailed below.
- Participants due a V11 (study primary endpoint) are asked to weigh themselves at home on scales provided by the study team. A working instruction has been provided to participants to support them to record their weight in a standardised manner. During virtual consultations, the study nurse or doctor may witness the weight measurement process (following receipt of verbal consent from the participant). In the absence of consent from the participant, the participant will report the weight measurement verbally and follow this up with a photo of the weight value (source data).
- A courier service has been arranged for study drug deliveries to participants; some sites are using a drop off/collection service either on site or to participant's homes. Participants on the Liraglutide arm will attend a virtual consultation and weigh themselves prior to additional study drug being dispensed.
- Participants in the Liraglutide arm who are of child bearing potential will receive a pregnancy test prior to their visit (to be used on the day of the visit) and the result reported either verbally to the study team during the video call or via a photo (source data) following a telephone call.
- The study quality of life questionnaire packs (HSRUQ, TSQM, EQ-5D, IWQOL-Lite, IPAQ-Long and PHQ-9) will be mailed to participants, where applicable, to be completed at home and returned to the study team via the postal system.

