As a result of conducting virtual consultations and telephone calls, the following procedures will not be performed during the COVID19 pandemic, therefore have been halted as an urgent safety measure:

- BP and Pulse measurements – Participants who are known to have hypertension have home BP monitoring machines and their BP measurements are being collected and assessed by the study team during remote visits. There is no undue risk for those who do not have hypertension, as Liraglutide is not related to BP, and participants are all established on the drug.
- Bloods (lipids, renal, LFTs, thyroid, FBC & HbA1c, amylase) at V9, 11 & 13/15 only - The amylase test usually taken at visits 9, 11 & 15 is a safety blood in relation to pancreatitis. During the remote visits, all participants will be monitored for any new symptoms which will be appropriately managed by the study clinical team. The small number of participants who have diabetes will regularly check their blood glucose at home as usual. All other bloods are taken to assess efficacy, therefore not conducting them will have no impact on participant safety. All participants will be asked to report AE/SAE during remote visits.
- ACR urine test – Not conducting this poses no additional risk to participants.

Once restrictions due to the COVID19 pandemic have been lifted, a further risk assessment will be completed and in agreement with the Sponsor, Study team and NHS Host Organisations, face to face visits will be re-implemented. For the avoidance of doubt, virtual consultations will still be an option for study visits, as preferred by the participant or recommended by the study clinician, to aid the retention of participants and study visit attendance and collection of primary outcome data (via self-reported weight measurement data).

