Proportion of those with diabetes at baseline with HbA1C<6.5%	52, 104	From HbA1c measurement, a binary indicator will be derived, being 1 if participant achieves the target and 0 if they do not.
Change in Albumin-Creatinine Ratio (ACR; mg/mmol) from baseline for participants with diabetes, prediabetes, or hypertension	52, 104	Follow-up ACR – baseline ACR, only for participants defined as having diabetes, prediabetes, or hypertension
Obesity-related co-morbidities and their treatments (Hypertension)		

Systolic blood pressure (mmHg)^b	52, 104	Follow-up systolic blood pressure – baseline systolic blood pressure
Diastolic blood pressure (mmHg)^b	52, 104	Follow-up diastolic blood pressure – baseline diastolic blood pressure
Hypertension	52, 104	Binary indicator of 1 if participant is on antihypertensive medications or systolic blood pressure > 140 mmHg ^c , 0 otherwise with baseline values also presented
Number of agents for hypertension	52, 104	Change from baseline in total number of medications taken for hypertension defined as medications in any of the following classes: ACE-inhibitors, calcium channel blockers, thiazide diuretics, alpha-blockers, and beta-blockers.
Obesity-related co-morbidities and their treatments (Dyslipidaemia)		
LDL cholesterol (mmol/L)	52, 104	Follow-up LDL cholesterol – baseline LDL cholesterol
HDL cholesterol (mmol/L)	52, 104	Follow-up HDL cholesterol – baseline HDL cholesterol
Total cholesterol (mmol/L)	52, 104	Follow-up total cholesterol – baseline total cholesterol
Triglycerides (mmol/L)	52, 104	Follow-up triglycerides – baseline triglycerides
Number of agents for dyslipidaemia	52, 104	Change from baseline in total number of medications taken for dyslipidaemia defined as medications in any of the following classes: statins, fibrates, and ezetimibe.
Number of participants referred for other obesity intervention		
Referred to Tier 4 for bariatric surgery	104	Binary indicator of 1 if participant was referred to Tier 4 for bariatric surgery over 104 week period, 0 otherwise
Treatment satisfaction		
Treatment	Satisfaction	Questionnaire for Medication (TSQM)
	52, 104	Change from baseline in TSQM scale score. Scored as per version II (detailed in Appendix B on vhe.066.fm (iqvia.com)).
Safety/adverse events		
Gastrointestinal symptoms	52, 104	Binary indicator of 1 if participant experienced any nausea or vomiting in study up until the time point of interest (captured in the expected AEs), 0 otherwise

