Stopped LIRA 3mg	16, 32, 52	Binary indicator of 1 if participant stopped treatment with LIRA 3mg at time-point (i.e., due to stopping rules or side effects), 0 otherwise. Only defined for participants in intervention arm who were on LIRA 3mg treatment at the previous time-point.
Completed 52 weeks of the Tier 3 service programme despite stopping LIRA 3mg at 16 weeks	52	Binary indicator of 1 if participant completed 52 weeks of the Tier 3 service programme despite stopping LIRA 3mg at 16 weeks, 0 otherwise. Only defined for participants in intervention arm who stopped LIRA 3mg treatment at 16 weeks.
Completed 52 weeks of Tier 3 service programme despite stopping LIRA 3mg at 32 weeks	52	Binary indicator of 1 if participant completed 52 weeks of the Tier 3 service programme despite stopping LIRA 3mg at 32 weeks, 0 otherwise. Only defined for participants in intervention arm who stopped LIRA 3mg treatment at 32 weeks.
Started on anti-obesity drugs	52, 104	Binary indicator of 1 if participant started on anti-obesity drugs other than LIRA 3mg, 0 otherwise. Defined as a concomitant medication listing of Orlistat.
Physical activity assessment		
International physical activity questionnaire (IPAQ- Long Form; MET-minutes/week)	52, 104	Total MET-minutes/week calculated in line with Appendix 6 and then change from baseline calculated.

^a Glucose lowering medications are defined as metformin, a sulphonylurea, a thiazolidinedione, or a SGLT-2.

^b These are also considered safety outcomes.

^c On the CRF, hypertension is a yes/no tick box with the following wording: "Hypertension treated (antihypertensives with or without diagnosis) or untreated (systolic blood pressure >140 mmHG at two consecutive visits to Tier 3 clinic)." If a definition of anti-hypertensive medications is required for the derivation of any variables then the following medication should be considered as anti-hypertensive: ACE-inhibitors, calcium channel blockers, thiazide diuretics, alpha-blockers (e.g., doxazosin) and beta-blockers.

N.B. CPAP compliance (hours/days) was listed as a secondary outcome in the protocol but will not be reported as it hasn't been captured in the database.

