15.2 Follow-up Glycaemic Status

Individuals are classified as having diabetes remission status if all the following is satisfied:

- Follow-up HbA1C <6.5%, not on glucose lowering medication for \geq 3months, have a previous medical history of diabetes and have NOT being on LIRA 3mg within the last 3 months

Individuals are classified as having diabetes status if one of the following is the satisfied:

- Follow-up HbA1C \geq 6.5%
- Have previous medical history of diabetes and they are on any glucose lowering medication (including Metformin) within the last 3 months and/or have being on LIRA 3mg within the last 3 months
- Are on any glucose-lowering medication except of Metformin (LIRA 3mg is considered obesity medication, not glucose-lowering)

Individuals are classified as having pre-diabetes status if one of the following is the satisfied:

- Follow-up HbA1C 6.0-6.4%, without previous medical history of diabetes and not on any glucose-lowering medication (but they can be on LIRA 3mg).
- Follow-up HbA1C 6.0-6.4%, without previous medical history of diabetes and only on Metformin from glucose lowering agents (and they can also be on LIRA 3mg).
- Follow-up HbA1C <6.0%, with a previous medical history of pre-diabetes (but without a previous medical history of diabetes) and only on Metformin from glucose-lowering agents (and they can also be on LIRA 3mg).

Individuals are classified as having Normoglycaemia if one of the following is the satisfied:

- Follow-up HbA1C <6.0%, without a previous medical history of diabetes and not on any glucose-lowering medication (but they can be on LIRA 3mg).
- Follow-up HbA1C <6.0%, without a previous medical history of diabetes or pre-diabetes and only on Metformin from glucose-lowering medications (and they can also be on LIRA 3mg).

16 Appendix 9: Templates for Tables

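### With no HbA1c and only selective blood pressure at remote visits, the SAP's rules for Hypertension and Glycaemic Status bias follow-up prevalence by an unknown amount

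*SAP*

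**What the plan says.** **Hypertension.** SAP 2.2.1 gives "Binary indicator of 1 if participant is on antihypertensive medications or systolic blood pressure > 140 mmHg", then "0 otherwise with baseline values also presented". No rule covers a participant who is off drugs and has no reading. Footnote c adds that "On the CRF, hypertension is a yes/no tick box with the following wording", but does not say whether status at weeks 52 and 104 comes from that box or from the derivation.

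**Glycaemic Status.** SAP Appendix 8 (15.2) has four categories and no default. Diabetes can be assigned without HbA1c. One route is "Have previous medical history of diabetes and they are on any glucose lowering medication (including Metformin) within the last 3 months", with recent LIRA 3mg use as an alternative to the drug. Another is use of any glucose-lowering agent other than metformin. Every route to remission, prediabetes or normoglycaemia needs an HbA1c.

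**Remote visits.** Protocol 8.10 states that "the following procedures will not be performed during the COVID19 pandemic" and lists blood pressure and pulse, bloods and urine ACR. The blood pressure exception is that "Participants who are known to have hypertension have home BP monitoring machines and their BP measurements are being collected". The blood tests dropped are "Bloods (lipids, renal, LFTs, thyroid, FBC & HbA1c, amylase) at V9, 11 & 13/15 only". V11 is week 52, and V13 or V15 (by arm) is week 104. Remote visits are not universal: "Face to face visits may continue at sites if this is in accordance with the local trust policy".

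**Handling of gaps.** Secondary outcomes use complete cases (SAP 3.3.1, 5.5.1), missing counts are reported (SAP 4.2), and template 16.10 has a *Missing* row for both outcomes. The SAP describes filling gaps from health records for weight only (1.2.1, 1.3).

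**The concern.** Both endpoints join a medication criterion, which can be known at any visit, to a measurement that was halted at remote visits. Whether a participant can be classified then depends partly on the status being estimated. Baseline values come from in-person visits, so part of any shift from baseline to week 52 or 104 could reflect who was classifiable.

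The two tables address the first secondary objective, improvement in obesity-related co-morbidities. The two obvious codings for Hypertension err in opposite directions, so a choice the SAP leaves open could change the apparent direction of change. The systolic and diastolic change rows have a related problem: at remote visits the follow-up value is a home reading from a known hypertensive, set against a baseline taken at a study visit, and nothing separates the two sources.

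**Working it through.** The plan gives no prevalence, treated share or remote share, so there is no figure of its own to reproduce. All inputs below are assumptions.

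**1. Who can be classified at a remote visit**

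- On antihypertensives: Hypertension = yes, with or without a reading.
- Off antihypertensives, known hypertensive with a home monitor: classifiable from the home reading.
- Off antihypertensives, not known to be hypertensive: no reading. The literal rule gives 0.
- Diabetes history with a glucose-lowering drug or LIRA 3mg in the last 3 months, or on a non-metformin agent: diabetes.
- Everyone else: Glycaemic Status cannot be assigned.

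**2. Hypertension**

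Let t = share on antihypertensives, u = share of the rest with SBP above 140 mmHg, and r = share of those off drugs who have no reading. Home readings in people off drugs make r smaller.

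- True prevalence = t + (1 − t)u
- Unmeasured coded 0 = t + (1 − t)(1 − r)u
- Unmeasured coded missing = [t + (1 − t)(1 − r)u] / [t + (1 − t)(1 − r)]

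With t = 0.55 and u = 0.15, true prevalence = 0.55 + 0.45 × 0.15 = 61.75%.

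| r | Coded 0 | Error | Coded missing | Error |
|---|---|---|---|---|
| 0.3 | 0.6175 − 0.3 × 0.0675 = 59.7% | −2.0 | 0.597/0.865 = 69.0% | +7.3 |
| 0.6 | 0.6175 − 0.6 × 0.0675 = 57.7% | −4.1 | 0.577/0.73 = 79.0% | +17.3 |

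Over a wider grid (t 0.4-0.7, u 0.1-0.3, r 0.25-0.75), coding 0 errs by −0.8 to −13.5 points and coding missing by +4.0 to +29.5 points. If the *Missing* row stays in the percentage denominator, the yes percentage equals the coded-0 figure.

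**3. Arm comparison**

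Take t = 0.5 and u = 0.2 in both arms (true prevalence 60%), with r = 0.6 in control and 0.4 in intervention. Coding missing gives 77.1% against 70.0%, a spurious gap of 7.1 points. Coding 0 gives 54.0% against 56.0%.

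**4. Glycaemic Status**

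Let d = share classifiable as diabetes without HbA1c, h = share with diabetes identifiable only by HbA1c, and r = share without HbA1c. Among those classified, diabetes = [d + h(1 − r)] / [d + (1 − d)(1 − r)].

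- d = 0.20, h = 0.03, r = 0.5: (0.20 + 0.015)/(0.20 + 0.40) = 35.8%, against a true 23%.
- d = 0.2-0.4, h = 0.05, r = 0.25-0.75: from 29.7% against a true 25% (+4.7 points) to 65.8% against a true 35% (+30.8 points).

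The LIRA 3mg route in practice exists only in the intervention arm. A remote participant with a diabetes history and no glucose-lowering drug is unclassified in control, but is classified as diabetes in the intervention arm if on LIRA 3mg within 3 months. The set of classifiable people therefore differs by arm.

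**5. Why any measured SBP is not enough**

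Suppose Hypertension required an SBP from any source, and all treated remote participants supplied home readings while nobody off drugs did. The result is [0.55r + 0.6175(1 − r)] / [0.55r + (1 − r)], which is again 69.0% at r = 0.3 and 79.0% at r = 0.6. Requiring an in-person SBP returns 61.75%, provided attendance is unrelated to status.

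**The case against.** The strongest reply is that the SAP already deals with missing data: complete cases, reported counts and a *Missing* row. The numbers of antihypertensive and diabetes agents are separate outcomes. Blood pressure change is follow-up minus baseline, so it is already paired and has its own count. Nothing here is tested, and every magnitude above is assumed. All of that is correct. It limits the impact but does not remove the defect, because the SAP does not say who enters the *Missing* row or whether that row counts in the percentage.

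Three stronger readings are tempting and are not supported:

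- *Every treatment of unmeasured values is wrong for both endpoints.* The default of 0 belongs to Hypertension only. HbA1c was halted at all remote visits, so setting Glycaemic Status to missing for everyone without one, whatever their medication, is unbiased if attendance is unrelated to status.
- *People who came off antihypertensives after losing weight are the ones miscoded.* They are generally known hypertensives, and Protocol 8.10 says that group has home monitors and is being measured. Those unmeasured are participants not known to be hypertensive. The reading fits diabetes better: someone now off glucose-lowering drugs and LIRA 3mg cannot be shown to be in remission without an HbA1c.
- *Many participants lack values.* The remote share is not given, and face-to-face visits could continue.

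**Conclusion.** The concern holds as a selective-classification problem of unknown size. Hypertension is understated if unmeasured participants off drugs are coded 0, and overstated if only they are set to missing. Diabetes is over-represented among those given a Glycaemic Status, and who can be classified differs by arm. Blood pressure change mixes home and study-visit readings without labelling them.

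The figures of 2-4 points low and 7-17 points high for Hypertension rest on 55% treated, 15% of the rest above 140 mmHg, and 30-60% of those off drugs unmeasured. None of these inputs is in the documents. Coding 0 is exact only if no unmeasured participant off drugs exceeds 140 mmHg.

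The effect is confined to descriptive secondary tables (SAP 5.5.1). The primary outcome, type I error and sample size are untouched. The change is still worth making, because the stated rules, applied as written, give biased answers on a named secondary objective and the repair is cheap.

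**What to change.** - **SAP Appendix 8 (15.2):** derive follow-up Glycaemic Status only for participants with an HbA1c at that time-point. Set all others to missing, whatever their medication.
- **SAP 2.2.1:** derive composite Hypertension only for participants with an in-person SBP at that time-point. Set all others to missing, and show home readings separately.
- **Table 16.10:** exclude the *Missing* row from the percentage denominator and show baseline for the same participants. Add rows for use of antihypertensive medication and of glucose-lowering medication, in all participants with medication data.
- **Table 16.11:** split blood pressure change into clinic and home follow-up readings.

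This costs SAP wording and a few table rows, with no new data. The SAP is marked as a draft and is to be finalised before database lock. The downside is a smaller denominator for the two composite outcomes. Their estimates would still assume that in-person attendance is unrelated to status, and the report should say so.

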- Proportion of participants with hypertension (defined as patients on antihypertensive medications or systolic blood pressure >140mmHg)
- Dose, class of medication, and number of agents for hypertension

Obesity-related co-morbidities and their treatments (Dyslipidaemia)

- Lipids
- Dose, class of medication, and number of agents for dyslipidaemia

Number of participants referred for other obesity intervention

- Number of participants referred to Tier 4 for bariatric surgery over the 104 weeks study period

Direct healthcare cost

- Frequency and cost of contact with General Practitioner (GP) (type and duration of contact will be recorded to enable use of Tariff prices from <http://www.pssru.ac.uk/project-pages/unit-costs/2016/index.php?file=full> to calculate accurate costings – accessed 21/07/2017)
- Frequency and cost of contact with Healthcare Professionals (HCP) (type and duration of contact will be recorded to enable use of Tariff prices from <http://www.pssru.ac.uk/project-pages/unit-costs/2016/index.php?file=full> to calculate accurate costings)
- Frequency of admissions, length of stay and cost of admissions to the hospital
- Frequency and cost of outpatient appointments with the hospital
- Prescription medication costs
- Health Service and Resources Use Questionnaire (HSRUQ)

Budget impact of Tier 3 service

- Cost of the proposed LIRA 3mg (as per protocol - e.g. actual dose taken = number of days taking study drug x daily cost of drug, or cost of total amount of study drug used)
- Cost of visits to clinician for assessment and medication prescription during Tier 3 programme
- Cost of visits to dietitian during Tier 3 programme
- Cost of visits to psychologist during Tier 3 programme
- Cost of exercise physiologist/physiotherapist during Tier 3 programme (if applicable)
- Cost of Multidisciplinary Team (MDT) discussion in Tier 3 service
- Cost of blood tests in Tier 3 service
- Cost of consumables and goods
- Cost of referral into Tier 4

Estimated cost-effectiveness of treatment over 2 years

- Length of treatment with LIRA 3mg
- Daily dose of LIRA 3mg (based on actual doses taken)

Safety/adverse events

- Gastrointestinal symptoms (nausea, vomiting)
- Overall hypoglycaemia rate
- Overall AE/SAE rate
- Rates of severe hypoglycaemia
- Heart rate
- Blood pressure

(See Section 10.4 for definitions of hypoglycaemia)

Treatment satisfaction

- Treatment Satisfaction Questionnaire for Medication (TSQM)

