7.2 Inclusion Criteria

To be considered eligible to participate in this study, a patient must:

- be aged between 18-75 years old (inclusive)
- understand written and spoken English
- be able to give informed consent
- have a BMI ≥ 35 kg/m 2
- have been referred to the Tier 3 service in one of the participating sites
- have a stable body weight (less than 5kg self-reported change during the previous 12 weeks)
- have at least one of prediabetes, diabetes, hypertension, and/or obstructive sleep apnoea, as defined below:
 - prediabetes (defined as established diagnosis of impaired fasting glycaemia (IFG) from GP and/or established diagnosis of impaired glucose tolerance (IGT) from GP and/or HbA1C 42-47 mmol/mol (6-6.4%) without glucose lowering medications, at a blood test during the last 6 months)
 - diabetes (defined as established diagnosis of Type 2 diabetes from GP and/or HbA1C ≥ 48 mmol/mol ($\geq 6.5\%$) at a blood test during the last 6 months] and/or being treated with any combination of lifestyle, metformin, sulphonylureas, Thiazolidinediones (TZDs) or SGLT-2)
 - hypertension treated (defined as being on antihypertensive treatment with or without a diagnosis of hypertension from GP) or untreated (defined as Systolic Blood Pressure ≥ 140 mmHg at two consecutive visits at the Tier 3 clinic),
 - obstructive sleep apnoea (on CPAP or established diagnosis of Apnoea Hypopnoea Index ≥ 15 at sleep studies during the last 12 months).

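### SAP 2.2.1 counts hypertension agents in five drug classes only, so receptor blockers and other unlisted antihypertensives are missed and a drug switch can look like de-escalation

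*SAP*

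**What the plan says.** **Agent count.** SAP 2.2.1 defines the number of agents for hypertension as the change from baseline in the number of medications in these classes: "ACE-inhibitors, calcium channel blockers, thiazide diuretics, alpha-blockers, and beta-blockers". The list has no category for anything else. The corresponding endpoint in Protocol 6.4.2 asks for dose, class and number of agents and names no classes.

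**Binary hypertension outcome.** SAP 2.2.1 gives: "Binary indicator of 1 if participant is on antihypertensive medications or systolic blood pressure > 140 mmHg". This follows Protocol 6.4.2: "Proportion of participants with hypertension (defined as patients on antihypertensive medications or systolic blood pressure >140mmHg". Neither row contains a class list.

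**Footnote c to SAP 2.2.1.** It describes the CRF item as a yes/no box covering treated hypertension, with no class limit, or untreated hypertension, worded as "systolic blood pressure >140 mmHG at two consecutive visits to Tier 3 clinic". It then adds a conditional rule: "If a definition of anti-hypertensive medications is required for the derivation of any variables then the following medication should be considered as anti-hypertensive", followed by the same five classes.

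**Entry.** Protocol 7.2 accepts treated hypertension as "being on antihypertensive treatment with or without a diagnosis of hypertension from GP", again with no class limit. It accepts untreated hypertension as a systolic pressure of 140 mmHg or more "at two consecutive visits at the Tier 3 clinic".

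**Declared changes and status.** SAP 5.8 lists departures from the protocol analysis, and the class restriction is not among them. SAP 5.5.1 makes the co-morbidity outcomes descriptive, with no formal testing.

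**The concern.** Improvement in hypertension is part of secondary objective 1, and a change in medication is one of the ways in which it would show. Protocol 8.5 leaves antihypertensive and diuretic recommendations to the local investigator in response to blood pressure and weight loss, and Protocol 9.6 asks for polypharmacy to be reconsidered after significant weight loss. The trial is open-label, so prescribing may change differently in the two arms.

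A closed list that omits a class of antihypertensive can fail in both directions. A switch out of a listed class looks like de-escalation, and a real stop of an unlisted drug looks like no change. Protocol 6.4.2 also asked for dose and class, but neither has a row in SAP 2.2.1, so the tables would not reveal that a lower count was only a switch. Footnote c could carry the same omission into the binary hypertension outcome, the baseline medication count (SAP 16.4) and the choice of who enters the ACR endpoint.

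**Working it through.** The plan states no figure to reproduce. The check sets the definitions side by side and then asks what the rule does to individual records.

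| Place | Drug part | Systolic part |
|---|---|---|
| Protocol 7.2, entry | any antihypertensive treatment | 140 or more, two visits |
| CRF box, per SAP footnote c | antihypertensives, no class limit | above 140, two visits |
| Protocol 6.4.2, outcome | antihypertensives, no class limit | above 140 |
| SAP 2.2.1, binary outcome | antihypertensives; five classes only if footnote c is invoked | above 140 |
| SAP 2.2.1, agent count | five classes, unconditional | not used |

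**Step 1: effect on the agent count.** That receptor blockers are antihypertensives is general pharmacology and is not stated in the documents. Call a drug outside the five classes unlisted. For each participant:

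counted change = true change − change in number of unlisted agents.

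- ACE inhibitor replaced by a receptor blocker: the true change is 1 − 1 = 0; the counted change is 0 − 1 = −1.
- Receptor blocker stopped: the true change is 0 − 1 = −1; the counted change is 0 − 0 = 0.
- Receptor blocker added: the true change is +1; the counted change is 0.

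The difference in mean change between arms is therefore wrong by the between-arm difference in mean change of unlisted agents. Applying one rule to both arms cancels the error only if unlisted drugs change equally in both.

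**Step 2: effect on the binary outcome, if footnote c is used.** A participant is wrongly coded 0 only if every antihypertensive taken is unlisted and systolic pressure is 140 or below. The same coding would remove that person from the ACR endpoint only if they had neither diabetes nor prediabetes, since either one also qualifies.

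**Step 3: scale.** The only input from the documents is N = 392. The rest are assumptions: 40% to 60% of participants treated, 5% to 20% of those on unlisted drugs alone, and 50% to 70% of those with systolic pressure of 140 or below. All 392 are taken as observed.

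- Treated but counted at zero agents: 392 × 0.40 × 0.05 = 7.8, up to 392 × 0.60 × 0.20 = 47.0.
- Coded non-hypertensive although treated, if the list is used: 7.84 × 0.50 = 3.9 (1.0% of 392), up to 47.04 × 0.70 = 32.9 (8.4%).

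Participants who take an unlisted drug alongside a listed one are undercounted too and are not in these figures.

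**Step 4: the 140 mmHg cut-off.** Moving between above 140 and 140 or more affects only untreated readings of exactly 140. For an assumed normal distribution with mean m and standard deviation s, their share is p = Φ((140.5 − m)/s) − Φ((139.5 − m)/s). With m from 125 to 140 and s from 12 to 18, p runs from 1.5% (m = 125, s = 12) to 3.3% (m = 140, s = 12). If a quarter of readings are rounded to the nearest 10, the share is 0.75p + 0.25[Φ((145 − m)/s) − Φ((135 − m)/s)], which is about 5% to 11%.

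**The case against.** A reader might infer that the SAP misclassifies hypertension outright and has also moved the blood-pressure cut-off. The documents do not support either reading.

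- The binary outcome row has no class list, and the CRF box has none. Footnote c applies its list only where a definition of antihypertensive medication is required. Drug misclassification of that outcome is therefore conditional on how it is derived.
- The cut-off of above 140 is the protocol's own outcome definition in 6.4.2, and the SAP copies it. An outcome need not match a two-visit entry criterion. Someone enrolled at exactly 140 is not automatically non-hypertensive at baseline, because blood pressure is measured again at the Baseline Visit (Protocol 8.3.1).

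Three further arguments limit the weight of the point. The endpoints are descriptive. The changes in systolic and diastolic pressure, also hypertension endpoints, do not use the drug list. Protocol 8.5 names antihypertensive drugs and diuretics as separate items, so leaving out non-thiazide diuretics could be deliberate, although the SAP does not say so.

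All of this stands, but none of it answers the agent count. There the five classes are the definition itself, with no condition attached, and they are narrower than the protocol without being declared.

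**Conclusion.** The point holds for the agent count as written: unlisted antihypertensives are not counted, and a switch from an ACE inhibitor to a receptor blocker appears as one agent fewer. For the binary hypertension outcome and ACR membership it holds only if footnote c is used in the derivation.

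The true size is unknown. The 8 to 47 and 4 to 33 participants out of 392 rest wholly on assumed treatment, drug-mix and control rates and show scale only. The direction of any between-arm error is also unknown, because it depends on how unlisted drugs change in each arm. The effect is confined to descriptive secondary tables, and the primary and anthropometric analyses are unaffected.

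The cut-off is a minor matter: the CRF wording (above 140) and the entry criterion (140 or more) disagree, which matters only for untreated readings of exactly 140.

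**What to change.** In SAP 2.2.1 and footnote c:

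- Add angiotensin-receptor blockers and an 'other antihypertensive' category. State by rule whether diuretics other than thiazides are counted.
- Code from recorded drug names. Protocol 9.6 has changes recorded by trade or generic name; the documents do not confirm that the indication is recorded, so the rule should not depend on it.
- Apply the same list at baseline and follow-up, and say whether it is used for the binary outcome and ACR membership.
- Keep the protocol's outcome cut-off of above 140. Derive baseline and follow-up status from medication and measured systolic pressure with that one rule, not from the CRF box.
- Record these changes in SAP 5.8.

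The entry criterion should be left alone: the amendment history puts the end of recruitment at 29/02/2020, and the SAP draft is dated 01/08/2022.

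The cost is SAP wording and a recode of medications already recorded, with no new data collection. Deriving status from measured pressure leaves it missing for untreated participants with no reading at a remote visit (Protocol 8.10), and their number should be reported.
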